**Table 3. Safety Assessments and Action Needed During Health-Smart Intervention Sessions.**

	Normal	Not Clinically Significant (Document as per study protocol)	Urgent (Notify PCP in <24 h)	Alert (Notify PCP Immediately)
Systolic BP (mm Hg)	90-130	130-160	Low: 80-90 w/o Sx*	Low: <90 w/ Sx or <80
			High: 160-180	High: >190
Diastolic BP (mm Hg)	70-90	60-94	Low: 50-60 w/o Sx High: 95-110	Low: <60 w/ Sx or <50 High: >110
LDL-c (mg/dl)	<100	100-190	>190	NA
Triglycerides (mg/dl)	<150	150-400	400-800	>800
Glucose (mg/dl)	80-125	70-140	Low: 60-70 High: 141-300	Low: <60 High: >300
Pulse	60-100	60-100	Low: < 59 w/o Sx High: >100 w/o Sx	Low: < 59 with Sx High: >100 with Sx

\*Sx = symptoms of low blood pressure or pulse such as light headedness, dizziness, syncope (fainting) near syncope, palpitations, headache, vision changes, chest pain, shortness of breath.

If the patient experiences a serious adverse event at any of the Health-Smart intervention sessions that occur outside the clinic or after clinic hours, the CHW will call 911 and

complete a Serious Adverse Event Form that will be sent to the patient's health care provider and to the PI.

**Participant Privacy and Confidentiality.** The following steps will be taken to protect participants' privacy and confidentiality:

- Prior to recruiting patients for this study, CHWs will complete the required HIPAA and CITI or NIH GCP trainings as required by the IRB as well as training on how to enroll participants and implement all aspects of the study intervention.
- All signed consent forms will be kept in a locked file cabinet in a locked office at the study team's office in Jacksonville ([name]).
- All electronic documents and data will be stored in secure, password-protected servers on the UF campus.
- All paper based study documents including patient surveys and data collection forms will be stored in a locked filing cabinet in a locked room in the Center for Health Equity and Quality Research office on UF Health Jax campus.

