**Compensation.** Participating patients can receive up to \$150 in gift cards by participating in each of the three Measurement Sessions. Specifically, they will receive a \$25 gift card after participating in the first Measurement Session (Baseline), a \$50 gift card six months later after participating in Health-Smart and the second Measurement Session (Month-6), and a \$75 gift card 12 months later after participating in the weight loss maintenance sessions with their physician and the third Measurement Session (Month-18).

**Participant Safety.** The data taken during the measurement sessions will also be used for safety measures. If a BP measurement is taken that is an alert value, as listed in the Table 3 below, repeat measurements will be taken per clinic protocol. An average of at least two measurements will be used to determine the appropriate plan of action. The machine that measures blood pressure often also provides a pulse rate reading. The patient's pulse rate is not an outcome measure in the study, but will be addressed if it is outside of the normal range. Total cholesterol, LDL- cholesterol, HDL-cholesterol, triglycerides, and HbA1c will be assessed through point of care (POC) testing, as specified in the Study Intervention section above. Based on the readings of these measurements, an appropriate plan of action will be taken. Table 3 below lists both Urgent (notify PCP within 24 hours) and Alert values (notify PCP immediately while patient is still in the office). If the patient has a result in the alert value range, the physician or non-physician provider will determine if 911 needs to be called.

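### Minor: Table 3 gives no action tier to a systolic reading above 180 up to 190, or to a pulse of 59

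*Combined protocol and SAP*

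**What the plan says.** The Participant Safety text in section 4 makes the Table 3 columns operative. Urgent means telling the primary care provider within 24 hours, and Alert means telling them at once, before the patient leaves. For a blood pressure "that is an alert value, as listed in the Table 3 below, repeat measurements will be taken per clinic protocol". The response then rests on a mean: "An average of at least two measurements will be used to determine the appropriate plan of action". The emergency decision is tied to the same column: "If the patient has a result in the alert value range, the physician or non-physician provider will determine if 911 needs to be called".

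The rows that matter here are:

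- **Systolic:** Normal 90-130; document-only 130-160; Urgent 80-90 without symptoms, or 160-180; Alert "Low: <90 w/ Sx or <80", or >190.
- **Diastolic:** Normal 70-90; document-only 60-94; Urgent 50-60 without symptoms, or 95-110; Alert "Low: <60 w/ Sx or <50", or >110.
- **Pulse:** Normal and document-only both 60-100; Urgent <59 or >100 without symptoms; Alert "Low: < 59 with Sx", or >100 with symptoms.

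For pulse, the text adds that it is not an outcome but "will be addressed if it is outside of the normal range".

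**The concern.** A tier table is there so that staff at 20 clinics respond alike to the same reading. Medical assistants take the blood pressure at the first two measurement sessions, so the table tells non-physician staff when to escalate. At a systolic of 185 it does not say whether to repeat the reading, notify within 24 hours, or notify at once and have a provider decide about 911. The readings on either side are assigned, and the unassigned band lies above the whole Urgent range, where a response is most clearly intended. The pulse row has the same defect at a single value.

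What is at stake is consistent handling of a few safety readings. Sample size, power and the primary analysis are untouched.

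**Working it through.** The plan states no figure to reproduce. The check is whether every value on each row falls in a column.

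**Inputs and reading rule.** All six rows of Table 3, taken as printed. Hyphenated ranges include both ends, which is the reading that leaves the fewest gaps. The signs < and > are strict. Whole numbers were checked with and without symptoms.

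**Systolic, high side.**
- 180: Urgent.
- 181 to 190: above the Urgent limit of 180, but not above the Alert limit of 190, so no column. That is 190 - 181 + 1 = 10 whole-number values.
- 191: Alert.

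Symptoms play no part on this side of the row. Reading the ranges as exclusive would not shrink the gap.

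**Pulse, low side.**
- 60: Normal.
- 59: below 60, so not Normal or document-only; not below 59, so neither Urgent nor Alert. No column, with or without symptoms.
- 58: Urgent without symptoms, Alert with them.

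**Other rows.** Diastolic, LDL, triglycerides and glucose have no whole-number gap.

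**Shared end-points.** Some values fall in both a non-notifying column and Urgent: systolic 90 without symptoms, systolic 160, diastolic 60 without symptoms, triglycerides 400 and glucose 70. With symptoms, systolic 90 matches Normal only and diastolic 60 matches document-only, because the Alert limits are strict (<90, <60). These are overlaps or edge cases, not gaps, and the table gives no tie-break.

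**Illustration of size.** Every distribution here is assumed, because the documents give none. Take 758 x 3 = 2,274 measurement sessions and normal distributions with a continuity correction.
- Systolic 181-190, mean 130, SD 17: 2,274 x [Φ((190.5 - 130)/17) - Φ((180.5 - 130)/17)] = about 3.0. The range is 1.1 to 7.2 for means of 125 to 135, and 0.8 to 10.3 for SDs of 15 to 20.
- Pulse 59, mean 75, SD 12: 2,274 x [Φ((59.5 - 75)/12) - Φ((58.5 - 75)/12)] = about 31. The range is 16 to 50 for means of 80 down to 70, and fewer if the machine gives no pulse.

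These show an order of magnitude only. The session count assumes no drop-out. It also leaves out the screening visit, where blood pressure is measured, and the Health-Smart sessions, to which the table's title refers. The figures are neither bounds nor estimates from trial data.

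**The case against.** The strongest reply is that little turns on this. Measurement-session blood pressures are taken in the physician's own clinic, and the text promises an appropriate response to the readings in general. Staff would very probably treat 185 as at least Urgent. A pulse of 59 is outside 60-100, so the text already requires that it be addressed. All of that stands, and it is why the point is minor. It does not supply the missing tier or its timing.

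A second reply is that the systolic gap may be one wrong digit. The other high limits join exactly (diastolic 110 and >110, triglycerides 800 and >800, glucose 300 and >300), and the systolic row is split over two lines in the text available for review. A misread digit cannot be excluded, and the sponsor can check it at once. The pulse slip does not depend on it.

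A reader might also infer that Table 3 ranks a symptomatic woman below a symptom-free one at systolic 90 or diastolic 60. The documents do not support that as a settled defect. It needs inclusive ranges and overlaps resolved upward. If overlaps resolve downward, or Urgent is taken to stop short of the shared value as the strict <90 and <60 suggest, no value is inverted. Ranges elsewhere in the table also overlap or nest, so it was not drafted as a strict partition. What remains is an unstated tie-break.

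**Conclusion.** The table is wrong as written at two places: systolic above 180 up to 190, and pulse 59. Neither depends on how shared end-points are read; both assume that the table was extracted correctly. The systolic gap matters more, because nothing elsewhere in the documents gives those readings a tier. The pulse gap is narrower, because action is promised and only its tier and timing are missing.

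The size is small: ten whole-number systolic values, one pulse value, and no effect on any analysis. A reader might infer that women in these bands would go without care. The documents do not support that; they leave the tier unstated, and a clinical response remains likely. The severity is minor.

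**What to change.** Edit Table 3, with the sponsor's clinicians confirming each bound:

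1. Close the systolic gap, either as Alert >180 or as Urgent 160-190.
2. Change both low pulse limits from <59 to <60.
3. Add a note that a reading in two columns (for example systolic 90 or 160, or diastolic 60) takes the higher action tier, and that Alert applies if symptoms are present at the shared low cut-point. The second half is needed: without it, the note would raise a symptom-free woman at systolic 90 to Urgent and leave a symptomatic one in Normal. Because it extends the symptomatic Alert limit to the cut-point itself, it is a clinical choice. Ending low Urgent below 90 and below 60 would also remove the overlap without moving the Alert limits.

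The cost is one table edit, plus any clinic form that copies it. No new data, visits or staff are needed. The downside is a small number of extra provider notifications, for which no maximum should be stated. Under the assumptions above, with diastolic mean 80 and SD 11, the count is 19.16 (systolic 90 plus diastolic 60) + 2.96 (systolic 181-190) + 31.09 (pulse 59) + 11.25 (systolic 160) = about 64. With each mean 5 lower it is 38.97 + 1.11 + 49.66 + 6.41 = about 96. Both totals leave out glucose 70 and triglycerides 400, which the note would also move to Urgent. A total that moves this much with assumed means is not a ceiling.

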## 5. Statistical Analysis

The primary outcome is change in body weight (weight loss and maintenance of weight loss) in BW patient participants at the 20 participating primary care clinics. The unit of randomization will be the primary care clinic. Each clinic will be randomized into one of the two weight loss maintenance conditions (PCCS-WLM and SB-WLM).

**Sample Size/Power.** To detect a weight-loss difference of 5 pounds (between two groups) with a standard deviation of 12.5 pounds with 80% power and a 5% significance level, we will include 20 clinics and 25 study participants per clinic. Based on our pilot data, an intra-class correlation of 0.05 among patients within a clinic is used in these calculations. Based on the power calculation above, a total of 500 participants (20 clinics x 25 patient participants per clinic) will be needed for final analyses. Assuming a 25% dropout rate of patients per clinic, we will need 34 patients per clinic; thus, 680 patients will be enrolled in the study. However, based on Wave 1 (which involves 7 clinics) patient participant drop-out rate, the number of participants per clinic will need to be increased for Wave 2 and 3 to an average of 40 patients per clinic. Thus, the maximum number of patient participants enrolled in the study will be 758. Consequently, each of the two study arms will have a maximum of 379 patient participants.

**Data Analysis.** [name] who has a doctorate in Biostatistics will perform data analysis. Analyses begin with numerical and visual summaries of baseline characteristics of the sample. Continuous variables will be summarized by means, standard deviations, and medians. Categorical variables will be summarized by frequencies and percentages. Visual summary may include graphs, charts and tables. The main outcome variable (weight change) will be analyzed using a 2-level hierarchical model within the framework of a linear mixed model. The 2 levels of hierarchy will be defined as patient-level and clinic-level. Data will be analyzed within the context of linear mixed model. Weight loss between 6 and 18 months will be evaluated and compared between groups by defining an appropriate contrast within the model. Similarly, weight loss from baseline to 6 months also will be estimated (but not compared) by defining a contrast. It is assumed that those participants with BMIs greater than 50 will lose weight at the same rate of those with BMIs between 30 and 50. However, we plan to analyze the weight loss rates in two ways: one with all of the participants in the analysis and another with BMIs greater than 50 excluded. Based on these two analyses, we

can see if the subset of participants with BMIs greater than 50 impacts the effect size. These data sets will be compared using a mixed model for categorical data (e.g., GLIMMIX procedure in SAS). Descriptive analysis will be used to evaluate the effect of age, BMI, poverty rate (according to zip code), insurance type, and HbA1c at baseline.

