**Participation in the 6-month Health-Smart weight loss program.** Within two months after completing Measurement Session 1, patients will begin the Health-Smart weight loss program. ***The 6-month clinic-adapted Health-Smart intervention is part of both comparators*** and includes the following components/strategies: (a) assessment of each

participant's motivators of and barriers to health-smart behaviors using the Motivators of and Barriers to Health-Smart Behaviors Inventory—which has been published by the study PI; (b) coaching by a trained CHW that involves using the inventory-identified motivators and barriers to facilitate the patient participant's goal-setting and identification of strategies to achieve their goals, teaching participants to monitor selected health-smart goals and related goal attainment strategies, reviewing the standard goals for all patients that include 5% weight loss and increasing or maintaining steps walked to meet the 10,000 steps per day walking goal, and facilitating a patient-family member/friend discussion during which the patient asks the family member/friend to engage in behaviors that will support the patient in implementing her health-smart goal achievement strategies; (c) three months of weekly group sessions and then 3 months of bi-weekly group sessions; (d) 150 minutes of physical activity each week via patient participant-arranged or CHW-arranged activities such as group walks and individual walking to achieve 10,000 steps per day, and/or other self-selected moderate physical activities, and documentation of the physical activities in addition to documenting steps walked. Furthermore, the walking steps should begin with any number of steps that can be walked without any physical discomfort (e.g., pain, difficulty breathing) and then gradually increased by a number of steps that can be walked without any physical discomfort. Additionally, for participants who cannot walk at all, the physical activity goal is to engage in any physical activity up to 150 minutes per week that does not cause any physical discomfort. During at least one of the sessions in the Health-Smart intervention, patient participants will be given the opportunity to anonymously or directly ask health-related questions to a panel of health experts (e.g., dietitians) and Black women community members who have lost weight and maintained this weight loss.

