**Measurement Session 2.** After the completion of the 6-month Health-Smart weight loss program, patients' weight, height, blood pressure will be measured by a Medical Assistant at their physician's clinic. Additionally, patients' blood will be drawn to assess their total cholesterol, LDL- cholesterol, HDL-cholesterol, triglycerides, glucose, and HbA1c and they will complete the questionnaires previously completed as part of Measurement Session 1. The research coordinators assigned to clinics will input the patients' biometric and lab data from the Health Data Log form and store it in the dedicated IRB research drive.

**Weight Loss Maintenance Support from Primary Care Physician.** During the 12 months after completing the 6-month Health-Smart weight loss program, patients will have quarterly visits with their physician (at no charge to the patients) so that the physician can provide counseling and support to the patients that is designed to help the patients continue to lose weight or maintain the weight loss that resulted from participating in the Health-Smart weight loss program. In this phase, two different 12-month weight maintenance programs implemented by physicians will be compared (PCCS-WLM program and SB-WLM program). Both the patient and the CHW will be blinded on which program the patient will be participating in. The clinics will be randomly assigned to one of these two programs. The PCCS-WLM program (Comparator 1) will be implemented by the physicians of the participating patients at 10 clinics in this study, and the SB-WLM (Comparator 2) will be implemented by the physicians of participating patients at a separate set of 10 clinics in the study. Both of these programs consist of patient-physician clinical encounters every three months over a 12-month period, during which physicians in each program will review each of their participating patient's clinic-tracked weight/BMI and implement evidence-based provider behavioral counseling strategies for weight-regain prevention with each of these patients. A summary form that includes the patient's weight loss goals and health-smart goals will be provided to the physician prior to their first maintenance visit.

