Patient Survey of Provider Weight Management Practices. This is an 18-item survey developed by the Oregon Rural Practice-based Research Network and the Oregon Health & Science University in collaboration with the Agency for Healthcare Research and Quality. Two items from the 18-item Patient Survey of Provider Weight Management Practices (items 8 and 13) will be used to measure participants' perceived levels of their physician's engagement in discussions of their weight and health behaviors.

Table 2 lists the measures that will be completed at each Measurement Session.

Category	Intervention-Phase Month		
	0	6	18
Informed Consent and Eligibility criteria	X		
Body weight (Primary outcome)	X	X	X
Patient Goals setting		X	
Physiological Measures		X	X
Lifestyle Change Behaviors		X	X
Psychological Measures		X	X
Measures of patient participants' satisfaction with Health-Smart			X

**CHW Integration.** To address the **third primary aim**, we will implement and evaluate the medical assistant led (MA-led) program designed to integrate the CHWs into the health care team so that these CHWs can implement the 6-month Health-Smart weight-loss program at these clinics. The Office Manager and MAs at each participating clinic will train and mentor the CHWs assigned to that clinic to become integrated into the health care team at that clinic. This training will be informed by the nationally recognized TeamSTEPPS Program^26—an evidence-based set of teamwork strategies and tools developed by the Agency for Healthcare Research and Quality and aimed at optimizing patient outcomes by improving communication and teamwork skills among health care professionals. CHW integration effectiveness will be assessed using ratings by CHWs, MAs, and physicians on the TeamSTEPPS Medical Office Survey of Patient Safety. In particular, two subscales from this survey (the Working in Your Medical Office subscale, and the Communication and Follow-up subscale) will be administered electronically using Qualtrics at the beginning of the project prior to TeamSTEPPS training and after the 6-month Health-Smart weight-loss program. The survey will be anonymous and no personal health information is collected.

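### Optional precision gain, not an error: prespecify that the continuous 6-18 month between-arm comparison adjusts for each patient's month-0 and month-6 weight

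*Combined protocol and SAP*

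**What the plan says.** Section 5 (Data Analysis) analyses weight change in a two-level linear mixed model, with patients within clinics. The comparison between programs is described in one sentence: "Weight loss between 6 and 18 months will be evaluated and compared between groups by defining an appropriate contrast within the model". The next says: "Similarly, weight loss from baseline to 6 months also will be estimated (but not compared) by defining a contrast". Baseline variables enter only here: "Descriptive analysis will be used to evaluate the effect of age, BMI, poverty rate (according to zip code), insurance type, and HbA1c at baseline". Neither month-0 nor month-6 weight is named as a covariate.

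Weight is nevertheless recorded at months 0, 6 and 18 (Section 4, Measurement Sessions 1 to 3, and Table 2). The first two measurements come before the maintenance programs, and on the weight-loss phase Section 4 states: "The 6-month clinic-adapted Health-Smart intervention is part of both comparators". On blinding it states: "Both the patient and the CHW will be blinded on which program the patient will be participating in".

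Section 5 (Sample Size/Power) plans 20 clinics with 25 analysed women each, to detect 5 lb with an SD of 12.5 lb, 80% power and 5% significance; "an intra-class correlation of 0.05 among patients within a clinic is used in these calculations". It mentions no covariate adjustment.

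**The concern.** The wording leaves the form of the contrast open. If the arm means are free at all three visits and the data are complete, the contrast reduces to a comparison of raw change scores. That ignores what a woman's starting weight and her loss during Health-Smart may say about her later change. The instruction to estimate but not compare the first six months is compatible with treating the arms as equal up to month 6, but it does not say so.

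With 10 clinics per arm, the number of clinics is the main limit on precision, so using weights already collected is one of the few free ways to add some. Fixing the choice in advance also removes any later choice between an adjusted and an unadjusted result.

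**Working it through.** **Inputs from the plan.** Difference 5 lb, SD 12.5 lb, ICC 0.05, 25 analysed women per clinic (Section 5); 10 clinics per arm (Section 4). A two-sided 5% test is assumed, since sidedness is not stated.

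**The plan's own figure.**
- Between-clinic variance: 0.05 × 12.5² = 7.81.
- Within-clinic variance: 0.95 × 12.5² = 148.44; divided by 25 this is 5.94.
- SE = sqrt[(2/10) × (7.81 + 5.94)] = 1.658 lb.
- Power for 5 lb, noncentral t on 2 × (10 − 1) = 18 df: 81.4%. Nine clinics per arm would give 76.6%, so 10 is the smallest number that reaches 80%.
- Detectable difference at 80% power: 4.91 lb.
- Clinic-level share of the variance: 7.81/(7.81 + 5.94) = 57%.

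The stated design reproduces.

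**With adjustment.** Let r be the correlation between early loss and later change. It is an assumption; the range shown is 0.1 to 0.5. Each case uses 18 df.
- Within-clinic variance falls only: SE = sqrt[0.2 × (7.81 + 5.94(1 − r²))].
- Variance falls at both levels: SE = sqrt[0.2 × (7.81 + 5.94)(1 − r²)].
- Adverse case, where early loss varies between clinics (assumed ICC 0.05) but has no clinic-level relation to later change: SE = sqrt[0.2 × (7.81(1 + r²) + 5.94(1 − r²))].

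| r | Within only: SE, power | Both levels: SE, power | Adverse: SE, power |
|---|---|---|---|
| 0.1 | 1.655, 81.5% | 1.650, 81.7% | 1.659, 81.3% |
| 0.2 | 1.644, 82.0% | 1.625, 82.9% | 1.663, 81.1% |
| 0.3 | 1.626, 82.8% | 1.582, 84.8% | 1.668, 80.9% |
| 0.4 | 1.600, 84.0% | 1.520, 87.5% | 1.676, 80.5% |
| 0.5 | 1.566, 85.5% | 1.436, 90.8% | 1.686, 80.1% |

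The detectable difference moves from 4.91 lb to 4.90-4.64 lb (within only) or 4.89-4.25 lb (both levels).

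**Do 18 df hold for the adjusted model?** Two simulations used a clinic random intercept, both weights as patient-level covariates, and t on 18 df.
- 4,000 trials per case: type I error was 4.8% with r = 0 and 5.0% with r = 0.3 at both levels. Power was 81.9% with uninformative weights (81.9% unadjusted), 85.4% at r = 0.5 within only, 90.5% at r = 0.5 at both levels, and 79.7% at r = 0.5 in the adverse case.
- 1,500 trials per case (assumed weight SD 40 lb, early-loss SD 10 lb): type I error was 4.6-5.7%. Power was 81.3% with uninformative weights (81.3% unadjusted), 84.9% at r = 0.3 and 91.3% at r = 0.5 at both levels, and 79.3% against 81.9% unadjusted in the adverse case.

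**Cost of a missing month-6 weight.** Such women leave a covariate-adjusted analysis. With nothing explained, 24 evaluable women per clinic give SE = sqrt[0.2 × (7.81 + 148.44/24)] = 1.673 lb and 80.7% power; 23 per clinic give 1.689 lb and 79.9%.

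**The case against.** The strongest objection is that nothing is broken. Under clinic randomization the unadjusted contrast is valid, it meets its power target, and an open phrase about a suitable contrast does not forbid conditioning. The gain rests on a correlation that the documents do not give. All of that stands, and it is why this is offered only as an option. A reader might infer from the missing covariate that the primary analysis is biased or underpowered; the 81.4% figure and the randomization do not support that.

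A second objection is that month-6 weight may not be a true baseline. The documents do not say when clinics are randomized relative to month 6, and the stated blinding covers patients and CHWs, not physicians or the medical assistants who measure weight. This stands as a caveat. Using month-6 weight rests on Health-Smart being the same in both arms.

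A third is that a joint model of all three weights, with arm means held equal at months 0 and 6 and clinic effects that differ by visit, would be better because it keeps women without a month-6 weight. A reader might take it to be interchangeable with covariate adjustment. It is not. It lets clinic-level slopes differ from patient-level slopes, so it behaves much like a regression on 20 clinic means with two covariates and costs about 2 clinic-level df (16 instead of 18). In a clinic-mean approximation, power was about 76% with uninformative weights and about 79% at r = 0.3 at both levels; it rose above the unadjusted figure only with a strong clinic-level correlation (86.3% at r = 0.5). If the month-6 arm means truly differed, the constraint would also bias the estimated 6-18 month change. It is therefore not suitable as the primary model here.

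**Conclusion.** The point holds as a cheap, optional improvement. Starting from 81.4%, patient-level adjustment gives 81.5-85.5% power if only within-clinic variance falls and 81.7-90.8% if variance falls at both levels, for an assumed r of 0.1 to 0.5. There is no gain if the weights are uninformative, or if the 12.5 lb SD is already an adjusted one, which Section 5 does not say. In the adverse case the loss is about 1 to 3 points (1.3 by formula at r = 0.5, up to 2.6 in simulation), which can bring power slightly below 80%.

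Two limits apply. Section 5 does not say whether the 5 lb and 12.5 lb refer to months 6-18 or 0-18; the figures here apply them to 6-18. A reader might also infer that the gain carries over to primary hypothesis 2 in Section 3. It does not: that hypothesis concerns the percentage of women who maintain or continue their loss, and these calculations cover only the continuous comparison in Section 5.

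**What to change.** Before month-18 data are seen, add to Section 5 (Data Analysis) that:
- the continuous between-arm comparison models month-18 weight (equivalently, 6-18 month change) in the linear mixed model, with program, patient-level month-0 weight and patient-level month-6 weight as fixed effects and a clinic random intercept;
- inference uses a t reference on the clinic-level df, about 18;
- a sensitivity analysis retains women without a month-6 weight, by a likelihood-based or imputation method that respects clinic clustering;
- the unadjusted contrast is reported as supportive.

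The same edit should state when clinics are randomized relative to the month-6 measurement, which interval the 5 lb and 12.5 lb describe, and whether the 12.5 lb SD is raw or adjusted.

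The cost is SAP wording and one sensitivity analysis, with no added patients, visits or measurements. The statistical price is the possible small power loss in the adverse case and the exclusion of women without a month-6 weight from the main model.

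### The planned BMI-above-50 comparison sets a data set against its own subset with a categorical-data model, so it tells little about the equal-rate assumption

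*Combined protocol and SAP*

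**What the plan says.** All of this stands in the protocol's section 5, Statistical Analysis.

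- **Main model.** "The main outcome variable (weight change) will be analyzed using a 2-level hierarchical model within the framework of a linear mixed model". The arms are compared on change between months 6 and 18. For the first phase, "weight loss from baseline to 6 months also will be estimated (but not compared) by defining a contrast".
- **Assumption.** The plan takes it that "those participants with BMIs greater than 50 will lose weight at the same rate of those with BMIs between 30 and 50".
- **Check.** Weight-loss rates are analysed in two ways, "one with all of the participants in the analysis and another with BMIs greater than 50 excluded". From these the investigators expect that they "can see if the subset of participants with BMIs greater than 50 impacts the effect size".
- **Comparison.** The next sentence reads: "These data sets will be compared using a mixed model for categorical data (e.g., GLIMMIX procedure in SAS".
- **Other use of BMI.** The data analysis paragraph closes with a descriptive look at the effect of several baseline factors, BMI among them, without a contrast or confidence interval.

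The sample-size paragraph works in pounds ("To detect a weight-loss difference of 5 pounds (between two groups) with a standard deviation of 12.5 pounds"). Section 3 uses a loss of at least 5% of baseline weight and, for the second hypothesis, the percentage of women who keep or extend their loss. The inclusion criteria in section 4 set no upper BMI limit, so women above 50 can enrol.

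**The concern.** Three features of the check do not fit together.

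1. **Outcome and model.** The outcome in that paragraph is continuous and already has a linear mixed model. A categorical-data model needs a categorical outcome, and none is named for this check.
2. **Overlap.** The restricted set is the full set minus the BMI-above-50 women. The two results share most of their patients and are strongly correlated.
3. **Meaning of rate.** No unit is given. Pounds, percent of baseline weight and proportion of responders all appear elsewhere in the protocol, and they can give different answers.

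What is at stake is false reassurance. Two nearly identical estimates, or a non-significant comparison between them, could be reported as support for the equal-rate assumption when neither says much about it.

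**Working it through.** **Inputs from section 5:** 20 clinics of 25 women (500 analysed, 250 per arm), difference 5 lb, SD 12.5 lb, 80% power, 5% level (taken as two-sided), and "an intra-class correlation of 0.05 among patients within a clinic is used in these calculations".

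**Assumptions, not in the documents:** the BMI-above-50 share f is 5%, 10% or 20% (25, 50 or 100 of 500 women) and equal across clinics and arms; the SD and ICC are the same for both phases and both BMI groups, except where varied below.

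**The plan's own figure.** Without clustering, 99 women per arm are needed. The design effect is 1 + 24 × 0.05 = 2.2, giving 99 × 2.2 = 218 per arm against 250 planned. Power at 250 per arm is 81.4% (t test, 18 df). The stated 80% is reproduced, and the calculation treats the outcome as continuous.

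**Size of the shift.** The full-sample effect is (1 − f) × (effect at BMI 30–50) + f × (effect at BMI above 50). Subtracting the restricted effect leaves

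shift = f × (subgroup difference).

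For a 5 lb difference this is 0.25, 0.5 and 1.0 lb.

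**Effect of the overlap** (clustering ignored). Variance of the full-sample arm effect: 4 × 12.5² / 500 = 1.25. Variance of the restricted effect: 1.25 / (1 − f). Because the sets are nested, the variance of their difference is the second minus the first. Treating them as independent adds the two instead.

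| Share f | Correlation | Correct SE of difference | SE if treated as independent | Shift needed to reject (1.96 × SE) | Subgroup difference implied (shift / f) |
|---|---|---|---|---|---|
| 5% | 0.97 | 0.26 lb | 1.60 lb | 3.14 lb | 63 lb |
| 10% | 0.95 | 0.37 lb | 1.62 lb | 3.18 lb | 32 lb |
| 20% | 0.89 | 0.56 lb | 1.68 lb | 3.29 lb | 16 lb |

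In 10,000 simulated null trials per share, the independent-samples version rejected 0 times at every share. With the overlap handled it rejected in 4.9%, 4.8% and 5.2%.

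**What a direct estimate would give.** Within-clinic variance is 0.95 × 12.5² = 148.44; clinic effects cancel in the comparison of BMI groups.

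- SE of the shift = √(2 × 148.44 × f / (250(1 − f))) = 0.250, 0.363, 0.545 lb.
- SE of the arm by BMI-group interaction = that SE / f = 5.00, 3.63, 2.72 lb.
- Interaction detectable with 80% power (2.80 × SE) = 14, 10 and 7.6 lb; 95% CI half-width (1.96 × SE) = 9.8, 7.1, 5.3 lb.
- SE of the BMI-group contrast for months 0 to 6 = √(148.44 × (1/(500f) + 1/(500(1 − f)))) = 2.50, 1.82, 1.36 lb; detectable 7.0, 5.1, 3.8 lb.
- If the within-clinic SD is 1.45 times larger above BMI 50 (about 55/38), the detectable values become 20, 14 and 10.5 lb for the interaction, and 10.0, 7.2 and 5.2 lb for months 0 to 6.

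**Scale.** At an assumed height of 1.63 m, BMI 55 is 322.2 lb and BMI 38 is 222.6 lb. A 5% loss is 16.1 lb and 11.1 lb, a gap of 5.0 lb (3.6 to 6.5 lb for heights of 1.58–1.68 m and mean BMIs of 53–57 against 36–40). Conversely, 11.1 lb lost from 322.2 lb is 3.45%. A non-zero loss cannot be equal on both scales.

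**The case against.** **The sentence may concern responders.** The text speaks of weight-loss rates and then of categorical data, and section 3 has endpoints that are percentages of participants. If rate means the proportion of responders, a categorical mixed model is suitable and the choice between pounds and percent largely falls away. Section 5 names no other model for those endpoints. This reading is possible, but it is not stated: the sentence follows directly on the two BMI analyses and names no binary endpoint. The data sets would be nested on this reading too.

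**The with/without analysis is legitimate.** This stands. It answers its stated question, whether the subset moves the effect size. With the overlap handled, shift / SE equals interaction / SE (for 5 lb: 1.0, 1.38 and 1.84), so both carry the same information. No test statistic is specified, and compared might mean only placed side by side. The fault lies in the sentence announcing a model-based comparison of the two sets.

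**BMI is also examined descriptively.** This is true, but no contrast or interval is planned, so the equal-rate assumption still has no direct estimate.

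**Stronger readings that the documents do not support.** A reader might infer that naming GLIMMIX is itself an error; it is not, since that procedure can also fit a normal outcome. A reader might also infer that the planned check would often reject equal rates merely because of the scale chosen. That would need a BMI-group test on months 0 to 6, which the plan does not contain, and the rejection frequency would depend heavily on an assumed SD.

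**Conclusion.** The point holds as a minor correction to a secondary check. As worded, the comparison pairs a categorical-data model with a continuous outcome and a data set with its own subset, without saying how shared patients are handled. If the sets were treated as independent, the subgroup difference would have to reach roughly 16 to 63 lb before the comparison rejected, against a design difference of 5 lb. A small shift mainly reflects a small share and is no evidence of equal rates.

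The figures rest on assumed shares of 5% to 20%, equal across clinics and arms, and on the SD and ICC of the sample-size paragraph. The overlap result concerns one possible implementation, as the plan specifies none. A reader might take the point to undermine the main arm comparison or the sample size. It does not: the month 6 to 18 contrast is separate from this check, and the power calculation reproduces.

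**What to change.** 1. Keep the analyses with and without BMI above 50 as a descriptive sensitivity analysis, and report the BMI-above-50 share beside them.
2. Delete the model-based comparison between the two data sets. In the existing linear mixed model, add a BMI-group term (above 50 against 30–50 at baseline) and estimate, each with a 95% CI, (a) the arm by BMI-group interaction on the month 6 to 18 contrast and (b) the BMI-group difference in loss from month 0 to month 6.
3. State whether rate means pounds, percent of baseline weight or proportion of responders.
4. If the categorical mixed model was meant for the responder endpoints of section 3 (at least 5% loss; loss maintained or continued at 18 months), assign it to them by name, with clinic as a random effect, rather than deleting it.

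The cost is SAP wording and two extra estimates, plus a repeat run if percent change is also reported. No new data are needed. The drawback is imprecision: the interaction detectable with 80% power is about 14, 10 and 7.6 lb at shares of 5%, 10% and 20%, and larger if weight change varies more above BMI 50. The plan should therefore say that these are estimates with intervals and that a non-significant result does not show equality.
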